4.0 STUDY DESIGN

General Design

This is a pilot study of utilizing SPECT/CT imaging with 99m Tc-SC to accurately identify and quantitate functional liver tissue on serial imaging in patients receiving RT or surgery for liver cancer. The long-term goals are to use functional imaging to improve risk stratification for selecting which patients should undergo aggressive local treatments with RT or surgery and to aid in RT planning by preferentially sparing functional liver tissue, thereby leading to reduced liver toxicity. There will be two cohorts of patients: those receiving RT (Cohort A) and those undergoing surgery (Cohort B). A total of 60 patients will be enrolled (Cohort A, n = 40; Cohort B, n = 20).

All patients will have a total of 3 SPECT/CT imaging with ^{99m}Tc-SC. The first scan in both cohorts will be routine medical care (not experimental) and will take place prior to initiation of RT or surgery. Two follow up scans will be part of the protocol. In cohort A, the first follow up scan will occur at mid-RT, and the second one about 1 month post-RT (prior to any potential anatomical liver changes). In cohort B, the first follow-up scan will occur 3-5 days postoperatively (prior to any potential liver hypertrophy), and the second one about 1 month post-operatively (when liver hypertrophy is expected to occur).

Endpoints

4.1.1 Primary Endpoints

a) In this study, patients with liver cancer will undergo SPECT/CT imaging with ^{99m}Tc-SC at the time of RT planning for cohort A and within 1-2 weeks prior to surgery for cohort B. All image datasets will be imported into MIM 6.0, and fused with the RT planning CT and radiation plan for cohort A and with the contrast-enhanced diagnostic CT or MRI scan.

To characterize whole-organ liver function, all pre-treatment SPECT/CT images will be analyzed for 1) ratios of maximum, mean, and total liver SC uptake relative to spleen SC uptake (L/S) and 2) volumetric SC parameters such as the functional liver volume (FLV) formed by 58% maximum image intensity threshold segmentation. Optimal image thresholds for SC SPECT parameter association to CTP classification (A vs. B/C class) will be interrogated by receiver-operator characteristic (ROC) analysis. Image thresholds that yield maximum AUC in quantitative parameters such as FLV ratio, L/S ratio, and their total liver function (TLF) product will be propagated to the remaining analyses. In cohort A receiving RT, planned dose-volume and dose-function metrics within the tumor-subtracted liver and functional liver volume(s) will

feature mean dose, $D_{xx\%}$ (the dose given to xx% of liver volume), V_{zz} (the liver volume which receives zz Gy), and fV_{zz} (the percentage of total liver function which receives zz Gy).

To characterize spatial distribution of functional liver, radiomics will be applied to SC SPECT/CT images via a locally-developed open source radiomics toolkit [33]. In addition to the whole-organ SC SPECT/CT metrics descried above, radiomic features will include intensity histogram features, along with a variety of textural features derived from co-occurrence matrices, neighborhood difference matrices, and zone size matrices [34-36].

As a validation step, these baseline SC imaging data will be correlated to indocyanine green (ICG) clearance in patients (in those who opt to undergo this study), which assesses liver function based on the rate of clearance of a contrast agent over serial blood draws, and is considered a standard assessment of global liver function. ICG is a water-soluble compound that is selectively taken up by hepatocytes and transported into the biliary system without undergoing metabolism [37]. ICG clearance, therefore, can be utilized as an index of functioning hepatocyte mass [38] and is correlated with prediction of liver dysfunction and mortality associated with surgical resection [39]. The retention rate of ICG 15 minutes after administration (ICG-R15), a ratio of the ICG concentration at 15 minutes to its initial concentration in the blood, will be used to benchmark SC uptake metrics against. Higher ICG-R15 rates indicate worse liver function and would be expected to be correlated with lower global SC uptake metrics.

Functional FLR will be generated by calculating the volume of liver within the optimal image threshold as defined above. Anatomic FLR will be delineated and calculated on CT or MRI images using portal and hepatic veins as landmarks for segmental division. Logistic regression analyses and Pearson chi-square test will be used to compare the ability to predict for PHLR between functional FLR and anatomic FLR.

b) Correlate *post-treatment* changes in SC uptake on SPECT/CT imaging with changes clinical liver function. Relative changes in the parameters identified at baseline will be tested for correlation to changes in clinical liver function, including CTP score and ALBI grade, as well as their individual constituents.

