1.0 INTRODUCTION

Title	Functional Liver Imaging with Sulfur Colloid SPECT/CT in Primary and Metastatic Liver Cancer Patients Receiving Liver-Directed Treatment: A Pilot Study
Short Title	Sulfur Colloid SPECT/CT for Liver Cancers
Phase	Pilot Study
Methodology	Single Arm Open-Label
Study Duration	4 years
Study Center(s)	University of Washington Medical Center
Objectives	Study the use of SPECT/CT imaging with ^{99m} Tc sulfur colloid to characterize functional liver in patients receiving liver-directed treatments for liver cancers, and characterize liver tissue response to these treatments. The long-term goal is to use functional liver imaging to personalize liver-directed therapies in liver cancer patients by improving risk stratification and reduce treatment-related hepatotoxicity.
Number of Subjects	60 evaluable subjects
Diagnosis and Main Inclusion Criteria	Patients diagnosed with primary (hepatocellular carcinoma, cholangiocarcinoma) and metastatic liver cancers receiving liver-directed therapies (external beam radiation therapy, surgery).
Study Product, Dose, Route, Regimen	99mTc sulfur colloid SPECT/CT scans
Duration of administration	Drug administration will consist of 3 SPECT/CT scans with ^{99m} Tc sulfur colloid (one baseline scan which is standard of care, two follow-up scans which are experimental and paid for by departmental research funds).
Statistical Methodology	^{99m} Tc sulfur colloid SPECT/CT parameters will be extracted, selected, and tested for statistical association to clinical liver function status and post-treatment toxicity using a variety of statistical methodologies. Receiver-operator characteristic (ROC) analysis will determine the optimal operating point for liver function classification accuracy using SC SPECT/CT parameters. Hypothesis testing of differences between independent groups will proceed using non-parametric Wilcoxon ranksum between 2 groups or Kruskal-Wallis ANOVA between >2 groups. Hypothesis testing of differences between imaging time points of the same subjects will proceed using non-parametric Wilcoxon sign-rank or Friedman ANOVA paired comparison. Survival analysis will consist of Kaplan-Meier estimation, log rank testing, and Cox proportional hazard regression. Dose-response models will be constructed from linear and logistic regression. Prediction models will utilize robust feature selection and feature fitting through multi-fold cross validation as part of a general machine learning framework.

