Technological advances in the field of radiation oncology have now made it possible to deliver high ablative or near-ablative doses of focal partial liver radiation with excellent local control rates of 70-90% after stereotactic body radiation therapy or proton beam therapy [2-4]. Similarly, advances in surgical techniques along with proper patient selection has allowed for encouraging 5-year overall survival rates of 50-70% despite more extensive resections [5]. Liver failure is the most serious and major cause of morbidity and mortality after treatment in HCC patients and arises primarily as a result of inadequate functional liver reserve post-treatment. Despite the most sophisticated radiation techniques, radiationinduced liver disease (RILD) can still develop in 5-67% of patients, depending on the baseline liver function and volume of liver irradiated, with fatal RILD in up to 5-7% [6-9]. Post-hepatectomy liver failure (PHLF) in resected HCC patients can occur in 5-20% of patients and is primarily dependent on the extent of resection and degree of pre-surgical liver dysfunction [10-12]. Potential reasons for the difficulties in mitigating these RILD and PHLF rates are the reliance on conventional assessments of liver function and on anatomical information of liver function to predict post-treatment liver toxicities. Furthermore, there are a group of patients that may not be offered potentially curative partial liver radiation or partial hepatectomy due to the fear of RILD or PHLF based on these crude conventional measurements of liver function and reserve post-treatment.

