3.0 STUDY OBJECTIVES

3.1 Primary Objectives

- a) Develop new quantitative metrics of baseline SC uptake on SPECT/CT imaging and correlate with clinical parameters of liver function and clinical outcomes in liver cancer patients receiving RT or surgery.
 - Hypothesis: Global metrics of baseline pre-treatment SC uptake on SPECT/CT imaging are more predictive for survival than conventional clinical measures of liver function and are associated with ICG clearance. For patients receiving surgery, the volume of the future liver remnant (FLR) as defined by SC SPECT/CT imaging (functional FLR) is more predictive for PHLF than CT-defined FLR volumes. Heterogeneity metrics of baseline SC uptake are associated with the severity of cirrhosis and prior liver-directed therapy; specifically, SC uptake within the liver is more heterogeneous in less compensated livers and in those that have received a higher number of liver-directed therapies.
- b) Correlate *post-treatment* changes in SC uptake on SPECT/CT imaging with changes clinical liver function.

Hypothesis: Changes in SC uptake between pre-RT and mid-RT/post-RT SPECT/CT scans are associated with changes in clinical liver function in response to RT and are predictive of liver toxicity at earlier time points compared to clinical assessments of liver function. SC uptake in the FLR (non-treated) is stable and preserved over time between pre-surgery and immediately post-surgery (3-5 days postoperative) scans.

Secondary Objectives

- a) Estimate the dose response relationship on multiple spatial scales (global liver, regional liver, liver image voxel) between radiation dose and changes in SC uptake, both acutely (mid-RT) and subacutely (1 month post-RT), using SC SPECT/CT imaging.
 - Hypothesis: Deficits in SC uptake due to absorbed dose is governed by a linear dose relationship. As the dose delivered to the region/voxel increases, the uptake in SC decreases in a linear fashion.
- b) Estimate the degree of radiation response in liver tissue with varying levels of function (i.e. compare radiation dose response of well compensated livers against less compensated livers).

This may establish a threshold of liver tissue that would be "safe" to treat without significantly affecting liver function.

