4.2.1 Primary Endpoints

a) Significant differences in Wilcoxon rank sum of ROC-optimized SC SPECT parameters will be tested between CTP classes. Spearman rank correlations between optimal SC SPECT parameters and clinical liver function parameters will be tabulated for the following categories: (1) composite liver function scoring systems (CTP score, ALBI grade), (2) individual quantitative liver function components (albumin, bilirubin, INR), and (3) individual qualitative clinical liver function components (encephalopathy, portal hypertension, ascites, and splenomegaly). Qualitative components will be treated as binary categorical variables (yes/no). Imaging and clinical parameters of liver function will be tested for association with overall survival. Continuous variables will be dichotomized above and below a threshold value that maximized accuracy of classification under ROC with balanced sensitivity and specificity. Univariate Cox proportional hazard regression will then be performed on all continuous and categorical variables. Statistically significant variables will serve as inputs into multivariate Cox proportional hazard regression. A stepwise backwards variable selection procedure will be followed to remove non-significant variables with high cross-correlation until the model log-likelihood is maximized.

Because radiomics generates feature sets of ~50 metrics, machine learning methods will be utilized to develop predictive models that are robust against overfitting, utilizing feature selection and classification/regression methods such as support vector machines, Bayesian analysis, and decision trees. These machine learning methods will be compared against standard statistical methods, such as ROC analysis and Kaplan-Meier estimation / Cox regression, for association to clinical liver function, prior liver-directed therapies, clinical outcomes (i.e. survival), and toxicity (i.e. CTP score progression).

b) The same set of statistical analysis will be performed for association of post-treatment changes in SC uptake on SPECT/CT imaging to clinical endpoints. Machine learning methods will test whether post-treatment changes in SC SPECT/CT provide independently predictive information after adjusting for baseline parameters.

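### The plan names no test that compares functional with anatomic FLR in the same 20 surgical patients, and the 1-4 PHLF events to be expected support exploratory estimation only

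*Combined protocol and SAP*

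**What the plan says.** Section 3.1, Primary Objectives (a), hypothesises that functional FLR "is more predictive for PHLF than CT-defined FLR volumes". This is a head-to-head claim about two predictors.

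Section 4.1.1 defines both as volumes. For the functional measure: "Functional FLR will be generated by calculating the volume of liver within the optimal image threshold as defined above". For the anatomic measure: "Anatomic FLR will be delineated and calculated on CT or MRI images using portal and hepatic veins as landmarks for segmental division". The comparison is then described in one sentence: "Logistic regression analyses and Pearson chi-square test will be used to compare the ability to predict for PHLR between functional FLR and anatomic FLR".

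That sentence does not say whether both measures enter one model, whether or where FLR is cut, or which statistic measures the difference. The statistical analysis text in section 4.2.1 mentions neither FLR nor PHLF. Its dichotomisation rule, "Continuous variables will be dichotomized above and below a threshold value that maximized accuracy of classification", belongs to the survival analysis. Paired methods appear only for time points, in the section 1.0 synopsis: "Hypothesis testing of differences between imaging time points of the same subjects will proceed using non-parametric Wilcoxon sign-rank or Friedman ANOVA paired comparison".

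Section 4.0 sets Cohort B at 20 patients. The only PHLF rate is in section 2.0: "Post-hepatectomy liver failure (PHLF) in resected HCC patients can occur in 5-20% of patients". No alpha, power or precision target is given for this comparison.

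**The concern.** Each surgical patient contributes both a functional and an anatomic FLR, so any comparison of their predictive ability is paired. A Pearson chi-square is built for independent groups. Used on the two sets of classifications, it ignores the pairing. Used once per predictor, it answers a different question, namely whether that predictor is associated with PHLF. The head-to-head hypothesis would then be judged informally, by setting one p-value beside another.

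Few PHLF events are also likely in 20 patients, so the large-sample approximations behind both named methods are in doubt. At stake is whether a statement that functional FLR is the better predictor would rest on an analysis able to support it.

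**Working it through.** The documents contain no sample-size or power derivation to reproduce.

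**Inputs.** n = 20 (section 4.0). PHLF rate p = 5-20% (section 2.0, resected HCC; section 5.0 also admits cholangiocarcinoma and metastases, so p is a proxy). Assumed, because the documents give no values: two-sided alpha 0.05, and the accuracies, AUCs and correlations stated below.

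**1. Expected events.** n × p = 20 × 0.05 = 1 to 20 × 0.20 = 4.

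**2. Distribution of events, Binomial(20, p).**

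| p | P(0) | P(1) | P(2) | P(0-2) |
|---|---|---|---|---|
| 5% | 0.358 | 0.377 | 0.189 | 0.925 |
| 10% | 0.122 | 0.270 | 0.285 | 0.677 |
| 20% | 0.012 | 0.058 | 0.137 | 0.206 |

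For example, P(2) at 5% = 190 × 0.05² × 0.95¹⁸ = 0.189.

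**3. Chi-square approximation.** With E events and m patients in the smaller FLR group, the expected event count in that group is E × m / 20. Since m is at most 10, this is at most E / 2, or 0.5 to 2.0 for 1 to 4 events. With at most 4 events in total, neither event cell can reach an expected count of 5, whatever the cut.

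Enumerating the true size of the nominal 5% test for one predictor, for p from 5% to 20%, gives 0.1% to 3.0% at a 10/10 split and 4.6% to 6.4% at a 3/17 split. The size depends on a cut that the plan does not state.

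**4. Reading A: the two sets of classifications compared as 20 versus 20 independent patients.** With both predictors 75% accurate (assumed), simulated size is 5.2% at correlation 0, 2.1% at 0.5 and 0.4% at 0.8. Ignoring the pairing makes the test conservative.

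**5. Reading B: one chi-square per predictor.** This gives two association tests and no test of the difference. To show how fragile the results are, take 4 events and a 10/10 split:
- 4-0 split of events: chi-square = 20 × (4×10 − 6×0)² / (10×10×4×16) = 5.0, p = 0.025 (Fisher's exact p = 0.087).
- 3-1 split of events: chi-square = 20 × (3×9 − 7×1)² / 6400 = 1.25, p = 0.26.

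Moving one event moves p from 0.26 to 0.025.

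**6. Logistic regression.** With both measures in one model there are at most 4 / 2 = 2 events per predictor, so separation is likely.

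**7. Does a paired test cure it?** It removes the mismatch but does not make a confirmatory test feasible.
- Exact McNemar on sensitivity with 4 events: the smallest two-sided p is 2 × 0.5⁴ = 0.125.
- DeLong paired AUC test (AUC 0.85 versus 0.70, correlation 0.5-0.8, assumed): power is about 16-21% with 4 events. With 2 events, type I error at equal AUCs of 0.70 is about 8-12%.
- At a 20% rate and correlation 0.5, power is about 69% at N = 100 (20 events) and 87% at N = 150 (30 events).

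**8. Bootstrap.** A plain patient-level resample contains no event with probability 0.95²⁰ = 36% if there was 1 event and 0.90²⁰ = 12% if there were 2, and the AUC is then undefined. Stratifying by PHLF status avoids this. The number of distinct resamples of k events is C(2k−1, k): 1, 3, 10 and 35 for k = 1 to 4. An interval with 1 or 2 events therefore means little, and with 3 or 4 it is still rough.

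**The case against.** The strongest reply is that this is a single-arm pilot with standard-of-care treatment, no alpha or decision rule is tied to this comparison, and the sentence names logistic regression first. One model containing both measures would respect the same-patient structure. These points stand, and they limit the severity. They do not supply a statistic for the difference, and the hypothesis is still listed as primary.

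Several stronger readings are tempting, and the documents do not support them:
- *The hypothesis rests on a chi-square alone.* It does not; logistic regression is named alongside it.
- *The chi-square is invalid at any sample size.* Run per predictor, with adequate counts and a prespecified cut, it validly tests association. It is simply not a comparison.
- *The method inflates false positives.* Under reading A it is conservative. Under reading B, simulations with two equally good predictors, a median split and exactly 4 events found just one predictor significant in roughly 21-39% of trials. That figure needs a median split the protocol never states, the top of the event range, and an informal comparison of p-values the protocol does not say it will make.
- *Two events can never give p < 0.05.* With both events in the smaller group, Pearson p is 0.136 at 10/10 and 0.068 at 8/12, but 0.042 at 7/13, 0.010 at 5/15 and 0.0004 at 3/17.
- *Six events would permit a superiority claim.* Six is where exact McNemar first reaches p < 0.05 (2 × 0.5⁶ = 0.031). It is not a threshold for an AUC comparison.

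**Conclusion.** The concern holds in a limited form. On either ordinary reading, the Pearson chi-square does not properly compare two predictors measured in the same patients, and the logistic regression has no stated measure of the difference. About 1 to 4 PHLF events are expected, too few for the chi-square approximation or for ordinary logistic regression with both predictors.

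The pairing point depends only on the design. The event count rests on applying an HCC rate to a mixed cohort. The size and power figures rest on the assumed accuracies, AUCs and correlations.

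The consequence is a low-power, hard-to-interpret comparison; inflation of type I error has not been shown as a general result. This should be fixed, but in a pilot with no decision tied to the comparison it is not a blocking fault.

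**What to change.** In section 4.1.1, replace the sentence on the comparison with a plan along these lines, and repeat it in section 4.2.1:
- Keep both FLR measures continuous. Report the within-patient difference in AUC for PHLF (functional minus anatomic), with an interval from a patient-level bootstrap stratified by PHLF status.
- Fit each FLR separately in a Firth-penalised logistic model.
- Label the comparison exploratory estimation, with no superiority claim at this cohort size.
- With 0-2 events, report the individual FLR values and outcomes descriptively, without an AUC interval.
- Correct PHLR to PHLF, and add an operational definition of PHLF, which the protocol lacks.

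The cost is a few sentences; no new patients, scans or visits are needed, and ROC analysis is already part of the plan. The claim becomes more modest, and the interval will be wide and approximate even with 3 or 4 events. The descriptive-only rule would apply with probability of about 92% at a 5% PHLF rate, 68% at 10% and 21% at 20%, so the sponsor should expect that this cohort may yield no formal comparison.

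### In the surgery cohort, the change analysis in primary endpoint (b) is confounded by extent of resection for the SC parameters that scale with liver volume

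*Combined protocol and SAP*

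**What the plan says.** Section 4.1.1(a) sets out the baseline parameters: "To characterize whole-organ liver function, all pre-treatment SPECT/CT images will be analyzed" for maximum, mean and total L/S and for "volumetric SC parameters such as the functional liver volume (FLV) formed by 58% maximum image intensity threshold segmentation". Image thresholds with the largest AUC in parameters such as "FLV ratio, L/S ratio, and their total liver function (TLF) product will be propagated to the remaining analyses". The denominator of the FLV ratio is not given. Section 2.0 (Clinical Data to Date) describes TLF as functional liver volume multiplied by mean liver-to-spleen uptake.

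Section 4.1.1(b) then states: "Relative changes in the parameters identified at baseline will be tested for correlation to changes in clinical liver function". The clinical side is CTP score, ALBI grade and their components. Section 4.2.1(b) adds: "The same set of statistical analysis will be performed for association of post-treatment changes in SC uptake on SPECT/CT imaging to clinical endpoints". Neither item separates the cohorts, names a region of interest for surgical patients, or includes a resection covariate. The only adjustment named is for baseline parameters, which are not listed, in the machine-learning step.

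Section 3.1(b) treats surgery differently. Its link between SC change and clinical change is worded for RT. Its one surgical hypothesis is at remnant level: "SC uptake in the FLR (non-treated) is stable and preserved over time" between the pre-operative and 3-5 day scans. Section 2.0 says that liver failure after hepatectomy "is primarily dependent on the extent of resection and degree of pre-surgical liver dysfunction".

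**The concern.** In Cohort B the two scans do not cover the same tissue. For a parameter that scales with the amount of liver, the relative change combines two things: how much functional liver was removed, and what happened to the tissue left behind. The plan's own hypothesis puts the second near zero at 3-5 days, so the better that hypothesis holds, the more completely the early change in these parameters reflects resection.

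Section 2.0 names extent of resection as a main driver of post-hepatectomy liver failure. If it also drives early change in CTP or ALBI, it acts on both sides of the planned correlation. A positive result in Cohort B could then be read as SC change tracking the function of liver tissue, when it shows only that larger resections are followed by worse clinical values. That matters here because the study's premise is that functional imaging adds to anatomical information.

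**Working it through.** **Inputs from the documents.** Cohort B has n=20 (section 4.0). The first post-operative scan is at 3-5 days, before regrowth. TLF = FLV × mean L/S (section 2.0). The documents give no resected fraction, no SD of uptake change, no correlation between resection and clinical change, and no alpha, so there is no stated figure to reproduce. Values for these are assumptions, shown as ranges.

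**Algebra.** Let r be the resected share of functional liver and d the relative change in uptake per unit of remnant. Take uptake as even across the liver and the spleen reference as unchanged.

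- FLV change: (1 − r) − 1 = −r
- TLF and total L/S change: (1 − r)(1 + d) − 1
- Mean L/S change: d
- Remnant relative to the same region before surgery, for total uptake: (1 − r)(1 + d)/(1 − r) − 1 = d

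With r = 0.40 and d = 0, TLF changes by 0.60 × 1 − 1 = −40% and mean L/S by 0%. With r = 0.40 and d = −0.05, TLF changes by 0.60 × 0.95 − 1 = −43%, of which 40 points are resection.

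**Mean change versus variation between patients.** With resected share uniform on 5-25%, 10-40% or 20-60% and a mean log change in remnant uptake of −0.10, resection makes up 62-84% of the mean log change in TLF. A correlation depends on variance between patients instead. There, resection's share, Var[log(1 − r)] / (Var[log(1 − r)] + SD²), runs from 5% to 80% for SDs of 0.10-0.30. It exceeds one half only at SD 0.10 with the two wider resection ranges (58% and 80%).

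**Large-sample correlations.** Let clinical change depend only on extent of resection, with correlation 0.3 or 0.5 and higher values meaning worse function. In the same scenarios Spearman's rho is −0.29 to −0.50 for FLV change, −0.07 to −0.45 for TLF change, and 0.00 (at most 0.01 in size) for mean L/S change.

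**At n=20.** With two-sided 0.05 assumed and Fisher's z with variance 1.06/(n − 3), the critical value is |rho| = tanh(1.96/√(17/1.06)) = 0.45, and 80% power needs about 0.60. Simulated trials used TLF change (1 − r)(1 + d) − 1, with d pure noise:

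- r 20-70%, SD of d 5%, resection-clinical correlation 0.6: mean rho −0.57, significant in about 79%.
- r 10-40%, SD 20%, correlation 0.5: mean rho −0.24, significant in about 18%.
- r 5-25%, SD 30%, correlation 0.3: mean rho −0.06, significant in about 5%.

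Within-remnant change gave mean rho of about 0 and about 5% significant throughout. That follows from assuming d unrelated to clinical change; it is not evidence about real remnants.

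**The case against.** The strongest reply is that losing functional liver is a real loss of global function. The plan treats whole-organ SC metrics as indices of global function and benchmarks them against ICG clearance, which it describes as reflecting hepatocyte mass. On that view, resection acting on clinical values through lost mass is a mechanism, and restricting to the remnant answers a different question, with a measure the plan itself expects to be stable. This stands. Whole-liver change remains reportable, provided it is described as total loss of functional mass.

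Other replies also have weight:

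- Mean and maximum L/S and many texture features do not scale with volume. They could still shift if the removed part was hotter or colder than the rest. An FLV ratio taken to anatomical volume would also be size-free, as would a TLF built on it.
- Section 3.1(b) is already at remnant level for surgery. The gap is that 4.1.1(b) and 4.2.1(b) do not carry this through.
- The unlisted baseline parameters used for adjustment might include functional or anatomic FLR. The text does not say so.
- The statement in section 2.0 concerns liver failure after hepatectomy, not change in CTP or ALBI, and also names pre-surgical dysfunction.
- The later scan includes regrowth, so its change is not resection alone.

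A reader might infer that CT volumetry of the removed tissue would give the same result. The documents do not support that: functional and anatomic shares coincide only if uptake is homogeneous, and the plan's premise is that it is not.

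**Conclusion.** The point holds for FLV, total L/S and FLV-based TLF in Cohort B. As written, their 3-5 day change includes the resected functional share whatever happens to uptake per mL. A correlation with clinical change is therefore confounded by extent of resection and cannot show that SC change adds to knowing how much liver was removed.

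The size is uncertain. Over assumed resected shares of 5-70%, remnant-uptake SDs of 5-30% and resection-clinical correlations of 0.3-0.6, resection alone yields significance in about 5% to about 80% of trials with n=20. The top of that range is a favourable case, not an expectation.

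A reader might go further and conclude that SC change in this cohort is mostly removed tissue and says nothing about liver function. The documents do not support that. They give no resected fraction, resection need not dominate the variance between patients, several parameters do not scale with volume, and lost mass is itself lost function.

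**What to change.** In 4.1.1(b) and 4.2.1(b):

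- Analyse Cohorts A and B separately.
- For Cohort B, make the main change measure the ratio of the post-operative remnant to the pre-operative FLR region, for uptake, FLV and TLF. This matches the hypothesis in 3.1(b).
- If whole-liver change in volume-scaling parameters is also reported for Cohort B, show it with and without adjustment for resected volume fraction. Describe it as total loss of functional mass, not change in tissue function.
- Define the denominator of the FLV ratio, so that it is clear which parameters scale with volume.
- Label volume change at the later scan as including regrowth. That scan is placed at about 1 month in sections 4.0 and 7.0 but at 6 months for Cohort B in 4.1.2; these passages must be reconciled.

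The cost is a wording change. FLR delineation is already planned in 4.1.1, and section 7.0 takes contrast CT with all three surgical scans, so no new data are needed. The downside is that registration error in carrying the FLR contour between scans adds some noise.
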